1 OVERVIEW

The purpose of the statistical analysis plan (SAP) is to ensure the credibility of the study results by pre-specifying statistical approaches for the analysis of this study. The SAP is intended to be a comprehensive and detailed description of strategy and statistical techniques to be used to realize the analysis of data for EFC15116 study.

This plan may be revised during the study to accommodate protocol amendments and to adapt to unexpected issues in study execution or data that affect planned analyses. These revisions will be based on blinded review of the study and data. This plan will be finalized prior to the final database lock.

1.1 Background and Rationale

Atopic dermatitis (AD) is a chronic/relapsing inflammatory skin disease characterized by intense pruritus (i.e., itchiness), xerosis (skin dryness), and eczematous lesions whose features include erythema, infiltration/papulation, oozing with crusting, excoriations, and lichenification. It is often associated with other atopic disorders, such as allergic rhinitis and asthma. Severe disease can be extremely disabling due to several factors: major psychological problems, significant sleep loss, and impaired quality of life (QOL) that lead to a high socioeconomic cost. An estimated 2% to 10% of adults worldwide are affected by AD.

The pathophysiology of AD is influenced by a complex interplay between inflammation, environmental factors, genetics and skin barrier dysfunction.

Skin-infiltrating lymphocytes are thought to play a pivotal role in the initiation and amplification of atopic inflammation. The key cells involved in the pathophysiologic mechanism of AD are classified into 4 general subgroups. First, dendritic cell subtypes including Langerhans cells and inflammatory dendritic epithelial cells polarize T-helper cells via Immunoglobulin E (IgE)- and non-IgE-mediated mechanisms. Dendritic cells in the skin take up and present allergens to lymphocytes, causing a Type 2 helper T cell (Th2) polarization and subsequent release of pro-inflammatory cytokines, which include interleukin (IL)-4, IL-5, and IL-13. The T-helper cells are the second group of cells. In acute exudative skin lesions, chemokine “C” receptor (CCR4+) Th2 cells are abundant and secrete cytokines IL-4, IL-13, and IL-5, whereas Type 1 helper T cells (Th1), which secrete interferon-gamma (IFN- γ), are also seen in chronic, lichenified lesions. Activated eosinophils are the third group of cells, causing local inflammation at lesional sites. Keratinocytes are the fourth cell-type involved in the pathophysiology of AD. These skin cells express high levels of the Th2 polarizing cytokine and thymic stromal lymphopoitin in AD lesions, which may amplify and sustain the allergic response.

The goal in treating AD is reducing skin inflammation. Therapy has been focused on trying to control the T helper cell response. Topical corticosteroids (TCS) are overwhelmingly the most frequently prescribed class of drugs. However, long-term application of TCS is not recommended because of the risk of skin atrophy, dyspigmentation, acneiform eruptions, and risks associated with systemic absorption. Topical calcineurin inhibitors (TCI) are generally effective and safe as short-term treatments, but concerns of skin malignancies and increased risk of lymphomas have

prompted regulatory authorities to require a warning regarding the long-term safety of topical tacrolimus and pimecrolimus in their prescribing information. Repeated application of any topical therapy over a long period of time or to large surface areas also leads to reduced patient compliance. First generation antihistamines are widely prescribed for acute symptomatic treatment of pruritus, although their effectiveness is limited and largely attributed to their sedating effect. Oral immunosuppressants and glucocorticoids are effective, but are sometimes associated with severe toxicity and side effects, thus limiting their use to short courses and/or intermittent therapy. Diabetes, hypertension, and osteoporosis are side effects associated with systemic corticosteroids and there is also the risk of rebound after steroid discontinuation.

Cyclosporine, a current therapy for severe AD in some regions, is a potent immunosuppressant affecting both humoral and cellular immune responses. This results in increased susceptibility to infections and decreased cancer immunosurveillance. Other commonly recognized toxicities include hypertension and impaired renal and hepatic function. In addition, cyclosporine interacts with other commonly used medicines potentially affecting their metabolism and effect. Patients' disease often rebounds when the treatment is stopped, especially after the administration of systemic glucocorticoids. Biological agents including anti-tumor necrosis factor (TNF) α (infliximab, etanercept), anti-IgE (omalizumab), anti-IL-5 (mepolizumab), and anti CD11a (efalizumab) have generally been ineffective in clinical trials. Therefore, there exists a significant unmet medical need for an alternative treatment for AD.

Up-regulation of IL-4 and IL-13 have been implicated as an important inflammatory component of AD disease progression. Dupilumab, a fully human monoclonal antibody, is directed against the IL-4 receptor alpha subunit (IL-4R α), which is a component of IL-4 receptors Type I and Type II, as well as the IL 13 receptor system. The binding of dupilumab to IL-4R α results in the blockade of both IL-4 and IL-13 signal transduction.

Dupilumab is being developed for the treatment of moderate-to-severe AD in patients intolerant of, or not adequately controlled with, topical treatments. This population includes patients who are often treated with systemic corticosteroids, as well as other non-selective immunosuppressants, including cyclosporine, which are associated with significant toxicities. Dupilumab is being developed as a potential alternative to oral corticosteroids, calcineurin inhibitors, and other systemic immunosuppressive drugs, which are used for treatment of AD patients and have numerous, considerable adverse drug reactions (ADRs), and may increase the risk of serious infection. A more focused immunomodulatory agent such as dupilumab may have more limited effects on the immune system and potentially fewer ADRs.

Data with dupilumab have, to date, demonstrated efficacy, safety, and tolerability in a patient population with moderate-to-severe AD. In global phase 2 and phase 3 studies, treatment with dupilumab monotherapy consistently and significantly cleared or reduced the extent and severity of AD lesions and relieved pruritus, with superior treatment effect to placebo demonstrated by an array of clinically relevant endpoints.

The dupilumab safety database consists of over 3000 patients exposed to dupilumab across all indications, including over 2500 in AD. Dupilumab was well tolerated and generally safe when used in patients with moderate-to-severe AD.

This is a phase 3, randomized, double-blind, placebo-controlled study to evaluate the efficacy and safety in Chinese adult patients with moderate-to-severe AD whose disease cannot be adequately

controlled with topical medications or for whom topical treatment is medically inadvisable. This study will generate information in Chinese AD patients regarding monotherapy with dupilumab compared to placebo. The choice of placebo as a control is appropriate for the objectives of this study, since it will provide the most robust assessment of the efficacy and safety of dupilumab. The dose regimen of subcutaneous (SC) dupilumab selected for this study is 300 mg every 2 weeks (q2w). The dose of dupilumab in this study were based on the efficacy and safety results from global pivotal Phase 3 studies (R668-AD-1334 and R668-AD-1416).

1.2 Study Objectives

1.2.1 Primary Objective

The primary objective of the study is to evaluate the efficacy of dupilumab monotherapy compared to placebo treatment in adult patients with moderate-to-severe AD.

1.2.2 Secondary Objectives

- To evaluate the safety of dupilumab monotherapy compared to placebo treatment in patients with moderate-to-severe AD.
- To evaluate the effect of dupilumab on improving patient reported outcomes (PROs)
- To evaluate dupilumab immunogenicity

1.2.3 Other Objectives

- To evaluate dupilumab systemic exposure

1.3 Modifications from the Statistical Section in the Final Protocol

Modifications from the Amended protocol 1 (final protocol)

1. concomitant medication/procedure

Any concomitant treatment is considered from the first dose of study drug in the SAP instead of the time of informed consent in the protocol.

2. Potentially clinically significant abnormality (PCSA)

PCSA is applied to clinical laboratory evaluations and vital signs in SAP, while PCSA was applied to ECG as well in the protocol.

1.4 Modification from the Previously Approved SAP

NA

2 INVESTIGATIONAL PLAN

2.1 Study Design and Randomization

This is a randomized, double-blind, placebo-controlled, parallel-group phase 3 study to evaluate the efficacy and safety of dupilumab monotherapy in adults with moderate-to-severe AD. The study period included 16-week treatment period 12-week follow-up. Eligible patients will be randomized in a 1:1 ratio to receive q2w SC injections of 300 mg dupilumab, or matching placebo. Randomization will be stratified by baseline disease severity (moderate [Investigator's Global Assessment (IGA) 3] versus severe [IGA 4] AD).

2.2 Sample Size and Power Considerations

A total of 160 patients (with a randomization ratio of 1:1, 80 patients in each of the dupilumab 300 mg q2w and the placebo groups) will be enrolled in this study.

[figure not shown]
The study will have 94% power to detect the difference between dupilumab and the placebo. It is based on the following assumptions:

- The percentages of patients who achieve an IGA score of 0 to 1 and a reduction from baseline ≥ 2 points at Week 16 are 37% and 12% for dupilumab and placebo, respectively.
- A two-sided continuity corrected Chi-square test with the significance level of 0.05.

Calculations were made using nQuery Advisor 7.0 Software.

2.3 Study Plan

The study consists of a screening period, a treatment period and a follow-up period as presented below:

¹ Patients will receive a loading dose of the IMP on Day 1 and then receive the IMP every two weeks during the subsequent 14 weeks.

IMP = investigational medicinal product, q2w = once every 2 weeks.

After providing informed consent, patients will be assessed for study eligibility at the screening visit. Patients will undergo screening for 7-35 days prior to randomization. During the screening period, treatments for AD will be washed out, as applicable, according to eligibility requirements.

Patients may be rescreened once if they fail the screening evaluation for reasons related to incidental transitory conditions. Patients will be required to apply moisturizers (emollients) at least twice daily for at least 7 days before randomization and continue throughout the study. However, to allow adequate assessment of skin dryness, moisturizers should not be applied on the area(s) of nonlesional skin designated for such assessments for at least 8 hours before each clinic visit.

Patients who continue to meet eligibility criteria at baseline will undergo Day 1/baseline assessments and will be randomized to receive q2w SC injections of 300 mg dupilumab following a loading dose of 600 mg on Day 1, or matching placebo (including doubling the amount of placebo on Day 1 to match the loading dose). Eligible patients must have a documented history of inadequate response or intolerance to treatment with topical AD medications. Following the initial dose of 600 mg, the investigational medicinal product (IMP) will be administered 300 mg at Weeks 2, 4, 6, 8, 10, 12, and 14. Patients will remain at the study site for a minimum of 30 minutes after each injection at the study site. Patients will have the option to self-administer the IMP (or have a caregiver administer the IMP) outside the study site during weeks in which no clinic visit is scheduled (ie, Weeks 6, 10, and 14). Patients (and/or caregivers) will be trained on injecting the IMP at Visit 2 (Day 1) through Visit 4 (Week 4), or until competency has been demonstrated. Patients who do not want to self-inject may have the clinic staff administer all the IMP injections in the clinic.

During the 16-week treatment period, patients will have study visits at Weeks 0, 2, 4, 8, 12, and 16. Safety laboratory tests, collection of samples for dupilumab concentrations and anti-drug antibodies (ADA), and clinical assessments will be performed at specified clinic visits as noted in the Schedule of Events ([Appendix 10.2](#)).

The end of treatment visit will occur at Week 16, 2 week after the last dose of study drug. The primary endpoint will be determined at Week 16.

Follow-up visits will occur every 4 weeks from Week 20 through Week 28. The duration of the 12-week follow-up period is based on the time expected for drug levels to reach below the lower limit of quantification in most patients after the last dose of dupilumab. The end of study visit will occur at Week 28.

3 ANALYSIS POPULATIONS

In accordance with guidance from the International Conference of Harmonization of Technical Requirements for Registration of Pharmaceuticals for Human Use ([ICH](#)) guideline ICH E9 Statistical Principles for Clinical Trials (1998), the following populations of analysis will be used for all statistical analyses.

3.1 Intent-to-treat Population

The intent-to-treat (ITT) population includes all randomized patients. Efficacy analyses will be based on the treatment allocated by the interactive response technology (IRT) at randomization (as randomized). This is the primary analysis population for efficacy analyses.

For any patient who was randomized more than once, only the data associated with the first randomization will be used in any analysis population. The safety experience associated with any later randomization will be assessed separately.

Patients who temporarily or permanently discontinue from the IMP and who do not withdraw from the study will be asked to return to the clinic for all remaining study visits and complete all study assessments per the study schedule.

3.2 Per Protocol Population

The per protocol (PP) population includes all patients in the ITT population except for those who are excluded because of major efficacy-related protocol violations.

A major efficacy-related protocol violation is one that may affect the interpretation of study efficacy results. The criteria of major efficacy-related protocol deviation are defined as following:

- Patients who did not receive treatment as randomized, which are defined as
 - patients on placebo but accidentally exposed to dupilumab,
 - patients on dupilumab receiving placebo whose compliance with the dupilumab injection is <80% by counting placebo injections as missing
- Any major violations of efficacy-related entry criteria ([Appendix 10.7](#))
 - Inclusion criteria 3, 4, 5 and 6
 - Exclusion criteria 3, 4, 5, 6, 7, 8 and 9
- The percentage of a patient's compliance with the IMP injection is <80% or >120% of the scheduled doses during the study treatment period
- Patients who were randomized more than once
- Patients who were randomized but not treated

Final determination of the PP population will be made in the blinded manner prior to the database lock.

3.3 Safety Population

The safety population consists all randomized patients who receive any IMP. Patients will be analyzed according to the treatment they actually received (as treated).

The actual treatment group is defined by the following rules:

- For patients on placebo but accidentally exposed to dupilumab, the treatment group allocation for as-treated analysis will be dupilumab
- For patients on dupilumab but accidentally received placebo, the actual treatment group allocation for as-treated analysis will be the treatment as randomized if at least one dose or part of a dose of dupilumab was received
- For patients on dupilumab but accidentally received placebo, the actual treatment group allocation for as-treated analysis will be placebo if the patient did not exposed to any dupilumab

In addition:

- Nonrandomized but treated patients will not be part of the safety population, but their safety data will be presented separately
- Randomized patients for whom it is unclear whether they took the IMP will be included in the safety population as randomized

Treatment compliance/administration and all clinical safety variables will be analyzed using the safety population.

The pre-treatment period is defined as the time from signing the informed consent form (ICF) to before the first dose of IMP. The treatment emergent period is defined as the time from first dose of IMP (Day 1) to the end of the study.

For safety summarizes, three analysis period are defined as follows:

- On-treatment period is defined as day 1 to the day of last dose of IMP + 14 days or early termination date from study, whichever comes first
- Follow-up period is defined as the last dose of IMP + 15 days to the date of the end of study
- Overall study period is defined as day 1 to the date of the end of study, consisting of both the treatment and follow-up periods

The safety population will be the basis for the analyses for the week 16 treatment period and overall study period; however, for the analyses for the follow-up period, only a subset of safety population will be included, which is defined as the patients who entered the follow-up and had at least one visit after week 16 treatment visit.

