10.1.5 Early Termination Visit

Patients who are withdrawn from the study before the primary endpoint visit (Week 16) will be asked to return to the clinic for 2 visits: once for early termination assessments, and again at Week 16 (primary endpoint visit), as described in [Section 10.1.2.6](#). Patients who are withdrawn from the study after the primary endpoint visit will be asked to return to the clinic for early termination assessments.

The following information will be collected:

- Concomitant medications/procedures
- AEs

The following procedures and assessments will be conducted:

- Pruritus NRS and pruritus categorical scale
- POEM
- DLQI
- EQ-5D
- Assess sick leave/missed school days
- Vital signs
- IGA
- EASI
- BSA
- Photograph AD area (select sites only)
- Weight
- Physical examination
- ECG
- Laboratory testing:
 - Hematology and chemistry

- Urinalysis
- Serum pregnancy test (WOCBP only)
[REDACTED]
[REDACTED]
- Functional dupilumab PK sample
- Anti-dupilumab antibody sample

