5.8.1 Analysis of Adverse Events

The number and proportion of patients will be summarized separately for the week 16 treatment period, the follow-up period and overall study period, described in [Section 3.3](#). The incidence tables will present by primary SOC (sorted by internationally agreed order for the dupilumab group), HLT, HLT and PT sorted in alphabetical order for each treatment group and selected subgroup, including the number (n) and percentage (%) of patients experiencing a TEAE. Multiple occurrences of the same event in the same patient will be counted only once in the tables within a treatment phase. The denominator for computation of percentages is the safety population within each treatment group.

TEAEs will also be summarized by severity and relationship to IMP for each treatment group, presented by primary SOC and PT.

The time to first TEAE of special interest (AESIs) during the week 16 treatment period will be assessed by Kaplan-Meier estimates (K-M plot). The time is defined as the date of first event – the date of first dose + 1. Patients without an event will be censored at the end of 16-week treatment period. Graphs of cumulative incidence rate over time will be presented by treatment group.

Listings will be provided for all TEAEs, SAEs, death and TEAEs leading to permanent treatment discontinuation by treatment group and patient. Flags will be used to indicate on-treatment death.

The following variables will be included in the listing:

- Patient ID
- Treatment group
- Age/sex/race
- SOC
- HLGT
- HLT
- PT
- Verbatim Term
- AE start date and end date/ongoing
- AE Duration
- Relationship of AE to study drug: unrelated or related
- Action taken: drug interrupted, dose reduced, drug withdrawn, drug not changed, dose increased, or not applicable
- Severity: using a 3-point scale (mild, moderate, or severe)
- Outcome: recovered or resolved, recovered or resolved with sequelae, recovering or resolving, not recovered or not resolved, fatal or unknown

Overall TEAE summary

The overall summary of TEAEs will be provided with number and proportions of patients with any:

- TEAE
- TEAE related to study drug
- TEAE by severity
- Serious TEAE
- TEAE of special interest (AESI)
- TEAE leading to death
- TEAE leading to permanent treatment discontinuation

AESI:

- Anaphylactic reactions
- Systemic or extensive hypersensitivity reactions
- Malignancy
- Helminthic infections
- Suicide-related events

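### For some patients who leave the study early, the SAP's on-treatment and follow-up periods do not join, so their later adverse events can miss both by-period tables

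*SAP*

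**What the plan says.** SAP 3.3 defines three safety analysis periods.

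- **On-treatment:** "day 1 to the day of last dose of IMP + 14 days or early termination date from study, whichever comes first".
- **Follow-up:** "Follow-up period is defined as the last dose of IMP + 15 days to the date of the end of study". The early termination date plays no part in this start.
- **Overall:** Day 1 to end of study, described as "consisting of both the treatment and follow-up periods".

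For follow-up analyses, 3.3 takes only a subset of the safety population: "the patients who entered the follow-up and had at least one visit after week 16 treatment visit".

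SAP 5.8.1 refers back to 3.3 and has AE counts "summarized separately for the week 16 treatment period, the follow-up period and overall study period". It gives the safety population of each arm as the denominator, with no exception for follow-up.

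The protocol collects AEs after an early stop. Section 10.1.5 asks patients withdrawn before Week 16 to come back twice: "once for early termination assessments, and again at Week 16 (primary endpoint visit"). AEs are recorded at both visits. Section 10.4.2 continues observation after the IMP is stopped, up to that patient's end of study.

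**The concern.** The overall period can consist of the other two only if every observed day falls in one of them. The two boundaries are set by different rules. One can be cut short by early termination, while the other always waits until last dose + 15 days. The subset rule then uses the Week 16 visit as its reference, although follow-up time is counted from each patient's own last dose.

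The patients exposed to this are those who leave the study early, possibly because of how they fared on treatment. If their later events enter neither by-period numerator, the treatment-period and follow-up AE tables are too low. The shortfall would be unequal between arms if early leaving differs by arm.

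**Working it through.** The plan states no figure on this point, so the check applies the SAP 3.3 rules day by day.

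**Inputs.** Week 14 is Day 99, Week 16 is Day 113 and Week 28 is Day 197 (Protocol Table 1). The period boundaries and subset rule come from SAP 3.3. The early-stop and termination days are illustrative assumptions.

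**Notation.** L = day of last dose, T = day of early termination, V = last day with AE data.

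- On-treatment ends at min(L + 14, T).
- Follow-up starts at L + 15.
- Gap (a), by date: when T falls less than 14 days after L and V is at least L + 14, the days in no period number 14 − (T − L).
- Gap (b), by the subset rule: with no visit after Week 16, the excluded follow-up days number V − (L + 14).

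**Planned course first.** With L = 99, on-treatment ends at 99 + 14 = Day 113 and follow-up runs from Day 114 to Day 197. That is 113 + 84 = 197 days with none unassigned, so the definitions work for a completer.

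| Patient | On-treatment | Follow-up by date | Admitted to follow-up tables under 3.3 | Days in neither table |
|---|---|---|---|---|
| Completer, L = 99 | 1-113 | 114-197 | yes | 0 |
| Stops IMP, L = 29, stays to Week 28 | 1-43 | 44-197 | yes | 0 |
| (a) L = 57, T = 60, returns Day 113 | 1-60 | 72-113 | no | 61-71 by date (11), plus 72-113 by the subset rule (42) |
| (b) L = 29, last visit Day 113 | 1-43 | 44-113 | no | 44-113 (70) |
| (b) L = 29, leaves Day 85 | 1-43 | 44-85 | no | 44-85 (42) |

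**Range of gap (a).** The example gives 14 − (60 − 57) = 11 days. The maximum is 13 days if termination is at least one day after the last dose, or 14 if it is on the same day. The gap is zero once termination is 14 or more days after the last dose.

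**Range of gap (b).** With Week 16 as the last visit, the excluded time is 113 − (L + 14) = 99 − L days. That is 98 days for L = 1, 70 for L = 29 and 14 for L = 85.

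**Dependence on the denominator.** If the patient in the third row were admitted to the follow-up tables, Days 72-113 would be counted but Days 61-71 would still belong to no period. Gap (a) is therefore a boundary problem and gap (b) a subset problem.

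**The case against.** The strongest reply is that few patients meet the conditions and that nothing disappears from the safety analysis. Much of this stands.

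- **Most early stoppers should be unaffected.** Patients who stop the IMP are asked to attend all remaining visits (Protocol 8.1.4.2, 8.2.2 and 10.3.4). If they attend one after Week 16, the + 14 and + 15 boundaries meet and no day is lost.
- **Gap (a) depends on an undefined term.** If end of study for a withdrawn patient is the termination date, there is no later day to assign. SAP 3.3 does not say so. That reading also has a cost: the overall and treatment-emergent periods both stop at end of study, so AEs recorded at the Week 16 return visit could fall outside those too. Gap (a) also needs the patient to come back, which the protocol only requests.
- **Gap (b) depends on which text governs.** If the safety-population denominator of 5.8.1 overrides the 3.3 subset, gap (b) closes.
- **A fixed window may have been intended.** Both sections speak of a week 16 treatment period. If that means Day 1 to Week 16 for everyone, it captures the example days in both gaps. But 3.3 defines no such window, and 5.8.1 points back to 3.3. A fixed window would also overlap with follow-up: a patient with last dose Day 29 who stays in the study would have Days 44-113 in both.

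A reader might infer that these AEs are lost from the safety evaluation. The documents do not support that: the overall-period table covers them up to end of study, and 5.8.1 lists all TEAEs, SAEs and deaths. A reader might also apply an assumed IMP discontinuation rate of, say, 5-20% to 80 patients per arm and report 4 to 16 affected. That is the wrong rate, because stopping the IMP alone triggers neither gap. It bounds gap (b) from above only if the assumed rate is right.

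**Conclusion.** The definitions in SAP 3.3 are inconsistent with each other for some early leavers. The statement that the overall period is made up of the other two is untrue for them.

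The date gap is at most 13 days per patient when termination follows the last dose by at least a day. It needs withdrawal less than 14 days after that dose, later AE data, and an end of study later than termination. The subset gap can be much longer (14 to 98 days for last doses from Day 85 back to Day 1, with Week 16 as the last visit). It needs an early IMP stop, no visit after Week 16, and the 3.3 subset rule taking precedence with no fixed Week 16 window.

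The consequence is confined to the two by-period AE tables, which would be too low. Overall AE incidence and the listings are unaffected. The documents give no rate of early stopping or withdrawal, so neither the number of patients nor any imbalance between arms can be calculated. The correction is worth making because the rules, as written, misallocate events and are cheap to repair.

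**What to change.** In SAP 3.3:

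1. End the on-treatment period at last dose + 14 days or the last date on which AEs are collected for that patient, whichever is first.
2. Start follow-up on the next day.
3. Include in the follow-up tables every safety-population patient with AE observation after their own on-treatment period, and show the observation time per arm.
4. Define end of study for withdrawn patients, including those who return at Week 16.

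In SAP 5.8.1, align the week 16 treatment period and the denominator with these definitions. The time-to-first-AESI analysis should follow, since it uses the same period name and censors at its end.

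With these rules, the gap (a) example becomes on-treatment Days 1-71 and follow-up Days 72-113. The first gap (b) example becomes Days 1-43 and 44-113. No day is unassigned in either.

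The cost is SAP wording and a change to the AE period flag, with no new data, and it can be done before database lock. The downside is that the follow-up table will include some off-drug time before Week 16, which is why observation time should be shown.
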